ANNEX 7. LIST OF ATC CODES FOR MEDICATIONS OF INTEREST TO AVOID WHILE TAKING TOFACITINIB

All codes will be verified and updated prior to study initiation.

Class of drug	Drug	ATC code
Biologics	Abatacept	L04AA24
	Adalimumab	L04AB04
	Anakinra	L04AC03
	Certolizumab	L04AB05
	Etanercept	L04AB01
	Golimumab	L04AB06
	Infliximab	L04AB02
	Ixekizumab	L04AC13
	Rituximab	L01XC02
	Secukinumab	L04AC10
	Sarilumab	L04AC14
	Tocilizumab	L04AC07
	Ustekinumab	L04AC05
	Vedolizumab	L04AA33
Conventional synthetic DMARDS	Gold preparation (sodium aurothiomalate)	M01CB01
(csDMARD)	Gold preparation (sodium aurotiosulfate)	M01CB02
	Gold preparation (auranofin)	M01CB03
	Gold preparation (aurothioglucose)	M01CB04
	Gold preparation (aurotioprol)	M01CB05
	Hydroxychloroquine	P01BA02
	Leflunomide	L04AA13
	Olsalazine	A07EC03
	Penicillamine	M01CC01
	Sulfasalazine	A07EC01
Targeted synthetic DMARDS	Apremilast	L04AA32
•	Baricitinib	L04AA37
	Upadacitinib	L04AA44
	Filgotinib	L04AA45
Other DMARDS	Balsalazide	A07EC04
	Olsalazine	A07EC03
	Sulfasalazinea ^a	A07EC01
Selected potent	6-Mercaptopurine	L01BB02
immunosuppressant	Azathioprinea ^a	L04AX01
	Cyclosporinea ^a	L04AD01
	Tacrolimus	L04AD02

a Denotes that the medicine may also be classified as a csDMARD. csDMARD = conventional synthetic DMARDS

ANNEX 8. LIST OF ATC CODES FOR ANTIHYPERTENSIVES

All codes will be reviewed and updated prior to study initiation.

Class of drug	Drug	ATC code
Antiadrenergic agents,	Rescinnamine	C02AA01
centrally acting	Reserpine	C02AA02
	Combinations of rauwolfia alkaloids	C02AA03
	Rauwolfia alkaloids, whole root	C02AA04
	Deserpidine	C02AA05
	Methoserpidine	C02AA06
	Bietaserpine	C02AA07
	Reserpine, combinations	C02AA52
	Combinations of rauwolfia alkoloids, combinations	C02AA53
	Bietaserpine, combinations	C02AA57
	Rescinnamine	C02AA01
	Methyldopa (levorotatory)	C02AB01
	Methyldopa (racemic)	C02AB02
	Clonidine	C02AC01
	Guanfacine	C02AC01
	Tolonidine	C02AC04
	Moxonidine	C02AC04
	Rilmenidine	C02AC06
Antiadrenergic agents,	Trimetaphan	C02BA01
ganglion-blocking	Mecamylamine	C02BR01
Antiadrenergic agents,	Prazosin	C02CA01
peripherally acting	Indoramin	C02CA02
peripherany acting	Trimazosin	C02CA03
	Doxazosin	C02CA04
	Urapidil	C02CA06
	Betanidine	C02CC01
	Guanethidine	C02CC02
	Guanoxan	C02CC03
	Debrisoquine	C02CC04
	Guanoclor	C02CC05
	Guanazodine	C02CC06
	Guanoxabenz	C02CC07
Arteriolar smooth muscle,	Diazoxide	C02DA01
agents acting on	Dihydralazine	C02DB01
	Hydralazine	C02DB02
	Endralazine	C02DB03
	Cadralazine	C02DB04
	Minoxidil	C02DC01
	Nitroprusside	C02DD01
	Pinacidil	C02DG01
Other antihypertensives	Veratrum	C02KA01
J. F	Metirosine	C02KB01
	Pargyline	C02KC01
	Ketanserin	C02KD01
	Bosentan	C02KX01

1 10toco1 version 4.0, 20 1 columny 2024
Protocol version 4.0, 26 February 2024
113721403 HOLL HILLEN LITTLE STODI TROTOCOL

Class of drug	Drug	ATC code
	Ambrisentan	C02KX02
	Sitaxentan	C02KX03
	Macitentan	C02KX04
	Riociguat	C02KX05
	Ambrisentan and tadalafil	C02KX52

ANNEX 9. LIST OF ATC CODES FOR ANTIHYPERLIPIDAEMICS

All codes will be reviewed and updated prior to study initiation.

Class of drug	Drug	ATC code
Lipid modifying agents, plain	Simvastatin	C10AA01
	Lovastatin	C10AA02
	Pravastatin	C10AA03
	Fluvastatin	C10AA04
	Atorvastatin	C10AA05
	Cerivastatin	C10AA06
	Rosuvastatin	C10AA07
	Pitavastatin	C10AA08
	Clofibrate	C10AB01
	Bezafibrate	C10AB02
	Aluminium clofibrate	C10AB03
	Gemfibrozil	C10AB04
	Fenofibrate	C10AB05
	Simfibrate	C10AB06
	Ronifibrate	C10AB07
	Ciprofibrate	C10AB08
	Etofibrate	C10AB09
	Clofibride	C10AB10
	Choline fenofibrate	C10AB11
	Clofibrate	C10AB01
	Colestyramine	C10AC01
	Colestipol	C10AC02
	Colextran	C10AC03
	Colesevelam	C10AC04
	Niceritrol	C10AD01
	Nicotinic acid	C10AD02
	Nicofuranose	C10AD03
	Aluminium nicotinate	C10AD04
	Nicotinyl alcohol (pyridylcarbinol)	C10AD05
	Acipimox	C10AD06
	Nicotinic acid, combinations	C10AD52
	Dextrothyroxine	C10AX01
	Probucol	C10AX02
	Tiadenol	C10AX03
	Meglutol	C10AX05
	Omega-3-triglycerides incl. other esters and	C10AX06
	acids	
	Magnesium pyridoxal 5-phosphate glutamate	C10AX07
	Policosanol	C10AX08
	Ezetimibe	C10AX09
	Alipogene tiparvovec	C10AX10
	Mipomersen	C10AX11
	Lomitapide	C10AX12
	Evolocumab	C10AX13
	Alirocumab	C10AX14
	Bempedoic acid	C10AX15

Tofacitinib (Xeljanz®) A3921403 NON-INTERVENTIONAL STUDY PROTOCOL Protocol version 4.0, 26 February 2024

Class of drug	Drug	ATC code
	Inclisiran	C10AX16
	Evinacumab	C10AX17
	Volanesorsen	C10AX18

ANNEX 10. LIST OF LABORATORY TEST CODES

Laboratory test	Label (French)	Biology code
Creatinine (serum	CLAIRANCE (RENALE) DE LA CREATININE	0407
or urine)	PROFIL ENZ PANCREATIQUE	1531
	(AMYLASEMIE+AMYLASÜRIE+EVENT CREATININEMIE)	
	SANG: CREATININE	0592
	SANG : UREE ET CREATININE	0593
	UR. : CREATININE (CREATININURIE)	0627
TB screening	MYCOBACTERIES : IDENTIF. BIOCH AUTRE QUE	0244
	MYCOBACTERIUM TUBERCULOSIS	
	MYCOBACTERIES: IDENTIFICATION BIOCHIMIQUE DE	0243
	MYCOBACTERIUM TUBERCULOSIS	
Viral hepatitis B	HEPATITE B (VHB) : SD : AC ANTIHBC IGM PAR EIA	0352
and C screening	HEPATITE B (VHB) : SD : AC ANTIHBC TOTAUX PAR EIA	0351
8	HEPATITE B (VHB) : SD : AC ANTIHBE PAR EIA	0354
	HEPATITE B (VHB) : SD : AC ANTIHBS (IGG OU IG TOTALES)	0323
	PAR EIA	0020
	HEPATITE B (VHB) : SD : AG HBE PAR EIA	0353
	HEPATITE B (VHB): SD: AG HBS PAR EIA	0322
	HEPATITE B (VHB): CONTROLE DE GUERISON	4712
	HEPATITE B (VHB): DEPISTAGE ET/OU DIAGNOSTIC	4500
	HEPATITE B (VHB): DEPISTAGE ET/OU DIAGNOSTIC IGM ANTI	4501
	HBC	7501
	HEPATITE B (VHB): GENOME (ADN) (VHB): HYBRIDATION	4120
	MOLECULAIRE	7120
	HEPATITE B (VHB): STATUT IMMUNITAIRE DANS LE CADRE	4714
	D'UNE VACCINATION.	7/17
	HEPATITE B (VHB): SUIVI D'UNE HEPATITE B CHRONIQUE	4711
	HEPATITE B (VHB): SURVEILLANCE DE LA GROSSESSE	4715
	HEPATITE B (VHB): SORVEILEANCE DE LA GROSSESSE HEPATITE B (VHB):SD CONTROLE AVANT VACCINATION:AC	4713
	ANTI HBS+AC ANTI HBC EIA	4/13
	HEPATITE B (VHB):SD INFECTION RECENTE:AG HBS+AC	4710
	ANTI-HBC IGM PAR EIA	4/10
	GENOME (ARN) VIRUS DE L'HEPATITE C (VHC) : HYBRID	4121
	MOLEC: DETECTION QUALITATIVE	4121
	GENOME (ARN) VIRUS DE L'HEPATITE C (VHC): HYBRID	4123
	MOLEC: DETECTION QUALITATIVE	4123
	HEPATITE C (VHC): DETECTION QUANTITATIVE GENOME	4124
	(ARN)	4124
	HEPATITE C (VHC): GENOTYPAGE DU VHC PAR BIOLOGIE	4125
	MOLECULAIRE	4123
		2705
	HEPATITE C (VHC) : SD DE CONTROLE	3785
	HEPATITE C (VHC) : SD DE DEPISTAGE : AC ANTI-VHC	3784
Haemoglobin	ELECTROPHORESE DE L'HEMOGLOBINE (CITRATE AGAR)	1114
laboratory testing	ELECTROPHORESE DE L'HEMOGLOBINE (GEL	1113
	POLYACRYLAMIDE) HEMOGRAMME Y COMPRIS PLAQUETTES (NFS , NFP)	1104
	HEMATOCRITE (HTE)	2108

Laboratory test	Label (French)	Biology
		code
Alanine	ALANINE AMINOTRANSFERASE (ALAT,TGP) (SANG)	0516
aminotransferase	ASPARTATE AMINOTRANSFERASE (ASAT,TGO)(SANG)	0517
and/or aspartate	TRANSAMINASES (ALAT ET ASAT, TGP ET TGO)(SANG)	0522
aminotransferase		
laboratory testing		
(i.e., liver function		
testing)		
Lipid panel (i.e.,	SANG: CHOLESTEROL TOTAL (CHOL)	0580
total cholesterol,	SANG: CHOLESTEROL-LDL (C-LDL)	2001
high-density	SANG: TRIGLYCERIDES (TG)	0590
lipoprotein [HDL],		
low-density		
lipoprotein [LDL]		
and triglycerides		
[TG]) laboratory		
testing		

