no use of an		Note: This definition will miss those who have one 10 mg
alternative therapy		BID prescription and the remaining prescriptions are 5 mg
(i.e., biologic) prior to		BID.
tofacitinib initiation		
A patient who has	Outcome:	Among UC patients, is defined as ≥ 1 prescription dispensing
known VTE, CV or	Adherence to	for a biologic (as identified by ATC codes) prior to the index
malignancy risk	recommended	tofacitinib dispensing and an ADD >10 mg in any of the
factors with an ADD	posology	intervals: Weeks 17-24, Weeks 25-32, Weeks 33-40 or
of >10 mg in Weeks		Weeks 41-48 of follow-up and ≥1 VTE, CV or malignancy
17-24, Weeks 25-32,		risk factors from baseline to Week 16.
Weeks 33-40 or		
Weeks 41-48 of		An ADD \geq 15 mg in the definition above will be used in a
follow-up and with		sensitivity analysis.
evidence of a		
diagnosis for UC but		
no use of an		
alternative therapy		
(i.e., biologic) prior to		
tofacitinib initiation		

Adherence to patient screening and laboratory monitoring prior to and during tofacitinib treatment

The following recommended screenings and monitoring will be assessed in the following time frames:

- In the 30 days prior to and including the day of tofacitinib initiation;
- In the 31 to 60 days prior to tofacitinib initiation;

Table 3. Operational definitions of study variables in Système National des Données de Santé

Donnees de Sante			Donnees	
	Variable	Role		Operational definition

- In the 61 to 90 days prior to tofacitinib initiation; and
- In the 91 to 180 days prior to tofacitinib initiation;

For patients with at least 6 months of tofacitinib therapy (duration of tofacitinib therapy defined in Section 9.3.2):

- In the 60 days after the day of tofacitinib initiation;
- In the 61 to 120 days after tofacitinib initiation; and
- In the 121 to 180 days after to facitini binitiation.

For patients with 12 months of tofacitinib therapy (duration of tofacitinib therapy defined in Section 9.3.2):

- In the 181 to 240 days after tofacitinib initiation;
- In the 241 to 300 days after to facitinib initiation; and
- In the 301 to 360 days after to facitinib initiation.

For analyses, 1 month will be defined as 30 days and 1 year will be defined as 360 days.

List of laboratory codes in ANNEX 10. LIST OF LABORATORY TEST CODES.

List of laboratory codes	III THI TILL TO. LIDT	OF EMBORITORY TEST CODES.
Creatinine (serum or	Outcome:	Defined as ≥1 procedure code or ≥1 ICD-10 diagnosis code

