urine) laboratory	Screening	for a creatinine (serum or urine) laboratory test.
testing		
TB screening	Outcome:	Defined as ≥1 procedure code or ≥1 ICD-10 diagnosis code
•	Screening	for TB (active and latent) screening.
	Outcome:	
	Monitoring	
Viral hepatitis B and C	Outcome:	Defined as ≥1 procedure code or ≥1 ICD-10 diagnosis code
screening	Screening	for viral hepatitis B and C screening.
-	Outcome:	
	Monitoring	
Absolute lymphocyte	Outcome:	Defined as ≥1 procedure code or ≥1 ICD-10 diagnosis code
count (ALC)	Screening	for ALC laboratory testing.
laboratory testing	Outcome:	
	Monitoring	
Absolute neutrophil	Outcome:	Defined as ≥1 procedure code or ≥1 ICD-10 diagnosis code
count (ANC)	Screening	for ANC laboratory testing.
laboratory testing	Outcome:	
	Monitoring	
Haemoglobin	Outcome:	Defined as ≥1 procedure code or ≥1 ICD-10 diagnosis code
laboratory testing	Screening	for haemoglobin laboratory testing.
	Outcome:	
	Monitoring	
Alanine	Outcome:	Defined as ≥1 procedure code or ≥1 ICD-10 diagnosis code
aminotransferase	Screening	for ALT and/or AST laboratory testing.
(ALT) and/or	Outcome:	
Aspartate	Monitoring	
aminotransferase		
(AST) laboratory		
testing		

Table 3. Operational definitions of study variables in Système National des Données de Santé

Variable	Role	Operational definition
Lipid panel (i.e., total	Outcome:	Defined as ≥1 procedure code or ≥1 ICD-10 diagnosis code
cholesterol, high-	Monitoring	for lipid panel laboratory testing.
density lipoprotein		
(HDL), low-density		
lipoprotein (LDL) and		
triglycerides (TG))		
laboratory testing		
Describe prescribing p	atterns over time: De	scribe changes in the utilisation of tofacitinib following the
		or use after the 2019 Article 20 referral, the 2021 signal
evaluation procedure,	and the 2022/2023 JA	Ki Article 20 referral
Adherence to recomme	endations for limitation	ons of use in patients with VTE risk factors (will be
stratified by VTE repo	rting period 1, 2, 3)	
Assessment of VTE risk	factors prior to initiati	on of tofacitinib
Prior VTE	Outcome: changes	Defined as ≥1 ICD-10 diagnosis code for VTE in the 12
	in use in patients	months prior to the index tofacitinib dispensing.
	with VTE risk	List of VTE codes in ANNEX 12. LIST OF DIAGNOSIS
	factors	CODES FOR VTE.
History of surgery,	Outcome: changes	Defined as ≥1 procedure code for a major surgery in the
major	in use in patients	3 months prior to the index tofacitinib dispensing.
	with VTE risk	
	factors	

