9.7.2.1. Adherence to the recommended posology per indication and duration of use

Average daily dose, as listed in Table 3 and defined in Section 9.3.3, will be reported for each of the pre-specified time intervals as a continuous and categorical variable and may be stratified by presence of ≥ 1 major VTE risk factor(s) in the 12 months prior to tofacitinib initiation, pending sufficient sample size.

Duration of tofacitinib therapy, as listed in Table 3 and defined in Section 9.3.2, will also be described, tabulated and stratified by approved indication group ("RA or PsA" and "UC") and age (i.e., <65 and ≥65 years).

The variables listed under 'Outcome: Adherence to recommended posology' in Table 3 will be described and tabulated.

9.7.2.2. Adherence to patient screening and laboratory monitoring prior to and during tofacitinib treatment

The proportion of patients with evidence of having received the recommended screenings prior to initiation of tofacitinib and recommended monitoring after initiation of tofacitinib, as listed in Table 3, will be described and tabulated.

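### Annex 10's preliminary list codes TB screening only with two mycobacterial identification tests, one of them for species other than M. tuberculosis, and with no latent-TB test, so TB-screening adherence would be under-ascertained

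*Protocol*

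**What the plan says.** In Section 9.3.1, Table 3, TB screening is both a screening and a monitoring outcome. The definition has two alternative routes, "Defined as ≥1 procedure code or ≥1 ICD-10 diagnosis code", and its target is stated as "for TB (active and latent) screening". The block heading above these outcomes gives the source of the laboratory codes: "List of laboratory codes in ANNEX 10. LIST OF LABORATORY TEST CODES".

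The TB row of Annex 10 contains two biology codes and nothing else:

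- 0244, whose label begins "MYCOBACTERIES : IDENTIF. BIOCH AUTRE QUE" and ends with the name Mycobacterium tuberculosis;
- 0243, whose label begins "MYCOBACTERIES: IDENTIFICATION BIOCHIMIQUE DE" and ends with the same name.

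Section 9.7.2.2 sets the reported quantity: "The proportion of patients with evidence of having received the recommended screenings prior to initiation of tofacitinib", with the matching proportion for monitoring afterwards.

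On the status of the lists, Section 9.3.1 calls the codes in Table 3 and the annexes preliminary and allows refinement in the SAP. Section 9.9.1.2 (Laboratory data) says that procedure codes for the screening tests will be confirmed with the database owner or local clinicians, and that the SAP will note any test for which no procedure code is available.

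**The concern.** The listed codes do not match the outcome they are meant to measure. Both labels describe identifying an organism. One of them excludes M. tuberculosis by name, so a claim for it is not evidence of TB screening. Nothing in the row corresponds to latent TB, which the definition expressly includes.

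Screening and laboratory monitoring are part of Primary Objective 2. Section 7 says that the study's results will help decide whether the risk-minimisation materials are effective. With this list, a patient screened by any unlisted test is counted as unscreened unless the ICD-10 route picks the patient up. A patient worked up for a non-tuberculous mycobacterium is counted as screened. A low percentage would then reflect the code list, yet could be read as prescriber behaviour.

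**Working it through.** The protocol states no TB-screening rate and no code sensitivity, so there is no figure to reproduce. The check is a comparison of texts, followed by an illustration under stated assumptions.

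**1. Target against codes**

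| Element | Table 3 | Annex 10, TB row |
|---|---|---|
| Active TB | included | 0243 names M. tuberculosis, as an identification test |
| Latent TB | included | no code |
| Species other than M. tuberculosis | not part of the outcome | 0244, by its own label |

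**2. Contrast within Annex 10.** The hepatitis row includes codes whose labels name screening (dépistage): 4500, 4501 and 3784, the last of these being "HEPATITE C (VHC) : SD DE DEPISTAGE : AC ANTI-VHC". The TB row has no such label.

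**3. The ICD-10 route.** No annex lists an ICD-10 code for TB screening. The tuberculosis entry in Annex 11 defines a comorbidity, not a screening act; its code cell is empty in the text at hand, and nothing here rests on that. Section 9.9.1.2 (Diagnoses) says that outpatient ICD-10 data come only from LTD registration. Such registration records a disease for which care is fully reimbursed, so an outpatient with a negative screen would not be expected to appear there. The route exists but should add little.

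**4. Illustration of size.** Let p be the true proportion screened, Se the combined sensitivity of both routes, and f the proportion of unscreened patients wrongly counted as screened.

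Observed proportion = Se × p + f × (1 − p)

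Assumptions, none of them in the documents: p = 30%, 60%, 90%; Se = 5% and 20%, with 80% as a contrast; f = 0.

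| Se | p = 30% | p = 60% | p = 90% |
|---|---|---|---|
| 5% | 0.05 × 0.30 = 1.5% | 0.05 × 0.60 = 3.0% | 0.05 × 0.90 = 4.5% |
| 20% | 0.20 × 0.30 = 6% | 0.20 × 0.60 = 12% | 0.20 × 0.90 = 18% |
| 80% | 0.80 × 0.30 = 24% | 0.80 × 0.60 = 48% | 0.80 × 0.90 = 72% |

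Taking f = 1% adds at most 0.01 × 0.70 = 0.7 percentage points. In this illustration the false counts from 0244 are therefore small beside the loss from missing tests.

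**5. Does the planned safeguard catch it?** The commitment in Section 9.9.1.2 to note an unavailable test applies where no procedure code exists. Annex 10 supplies two codes, so the outcome looks measurable and that provision need not be triggered. The confirmation step could still catch the error, but nothing in the protocol flags it.

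**The case against.** The strongest reply is that the list is provisional. Section 9.3.1 calls the annex codes preliminary and requires the sponsor's review or approval of all code lists before the study starts, and Section 9.9.1.2 promises confirmation for exactly these tests. Annex 10 lacks the line about review and updating that Annexes 3 to 9 carry, but Annexes 11 to 13 lack it too, and Section 9.3.1 covers the annexes generally. This stands: the protocol has not fixed the list, and the final list may be right. It does not make the stated list right.

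A second reply is that the definition also accepts an ICD-10 code. That is correct, and any statement of size has to allow for it. For the reasons in the working, it is unlikely to recover many screened patients.

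A third is that 0243 may be legitimate, since it names M. tuberculosis and the outcome covers active TB. This stands in part. It is a reason to justify 0243, not to rely on it alone.

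Finally, Section 9.7.2.2 promises only a description of patients with evidence of screening and does not say that a low figure will be called non-adherence. That is fair as to its wording, although the analysis sits under the heading of adherence to screening.

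**Conclusion.** The point holds as a code-list error in a Primary Objective 2 outcome. Followed as written, the list would substantially under-ascertain TB screening and would count some work-ups for other mycobacteria as screening. The direction rests on the labels in Annex 10 and the definition in Table 3. The size rests on an assumed sensitivity: about 1.5% to 18% observed for true screening of 30% to 90%, if sensitivity is 5% to 20%.

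A reader might infer that the reported proportion would be near zero whatever prescribers do. The documents do not support that: it needs a combined sensitivity of about 5% or less over both routes, which is plausible but stated nowhere. A reader might also infer that the two tests apply only to organisms already grown in culture. The labels say only biochemical identification. Neither reading is needed for the conclusion.

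**What to change.** - Remove 0244 from the TB-screening definition.
- Do not use 0243 as the only TB-screening code. Keep it only with a stated justification as evidence of testing for active TB.
- Add the SNDS biology, procedure or dispensing codes for the TB screening tests that the risk-minimisation materials recommend, confirmed with the database owner and local clinicians as Section 9.9.1.2 already plans. Those materials are not part of the documents at hand, so the tests are not named here.
- List the ICD-10 codes meant for the alternative route, or drop that route for this outcome.
- If SNDS has no usable code, report TB screening as not measurable, give no percentage, and say so in Section 9.9.

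The cost is an edit to Annex 10 and the SAP code list, plus the confirmation already planned. If usable codes exist in SNDS, no new data source is needed; whether they exist cannot be settled from the protocol.

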ANNEX 11. LIST OF CODES FOR COMORBIDITIES

Comorbidity	Definition	Codes (ICD-10 codes, ATC codes, CCAM procedure codes)
Hepatic impairment	Defined as ≥1 ICD-10 diagnosis code for hepatic impairment.	K71 and K72
Renal impairment	Defined as ≥1 ICD-10 diagnosis code for renal impairment or a combination of EBM service	Stage III, IV or V (end stage) Chronic kidney disease
	codes, ICD-10 diagnosis codes and/or ICD-10 procedure codes.	ICD-10 diagnosis: Specific diagnoses of CKD Stage 3: N183 Stage 4: N184 Stage 5: N185 Other chronic renal disease: N188 and N189
		Diagnoses linked to CKD stage 5 Hypertensive cardionephropathy, with renal failure: I131 and I132 Extra-corporeal dialysis: Z491 Preparatory care for dialysis: Z490 Failure and rejection of a kidney transplant: T861 Dependence to kidney dialysis: Z992+1
		CCAM codes for medical procedures due to kidney failure (stage 5): JVJF002, JVJF004, JVJF003, JVJF005, JVJF006, JVJF007, JVJF008, JVRP004, JVRP007, JVRP008 and YYYY007 [TBC IN LAST VERSION]
Diabetes	Defined as ≥1 ICD-10 diagnosis code for diabetes or at least 3 reimbursements (or at least 2 in case of large pack sizes) of oral antidiabetes agents and/or insulin.	ICD-10 diagnosis: E10-E14 ATC code medications: A10*
Herpes zoster	Defined as ≥1 ICD-10 diagnosis code for herpes zoster.	B02*
Human immunodeficiency virus	Defined as ≥1 ICD-10 diagnosis code for human immunodeficiency virus.	B20-B24 and Z21
Tuberculosis, including both active and latent TB	Defined as ≥1 ICD-10 diagnosis code for tuberculosis.	
Viral hepatitis B or C	Defined as ≥1 ICD-10 diagnosis code for viral hepatitis B or C.	B180, B181 and B182

Comorbidity	Definition	Codes (ICD-10 codes, ATC codes, CCAM procedure codes)
Diverticulitis	Defined as ≥1 ICD-10 diagnosis code for diverticulitis.	Q396, Q696, K225, K382, N323, Q430, K314, N361 and C173
Malignancy (non-metastatic and metastatic, excluding non-melanoma skin cancer)	Defined as ≥1 ICD-10 diagnosis code for a malignancy (excluding non-melanoma skin cancer).	See table below
Non-melanoma skin cancer	Defined as ≥1 ICD-10 diagnosis code for non-melanoma skin cancer.	C44 other malignant tumour of the skin
Gastrointestinal perforation	Defined as ≥1 ICD-10 diagnosis code for gastrointestinal perforation.	K285
Hypertension	Defined as ≥1 ICD-10 diagnosis code for hypertension or at least 3 reimbursements (or at least 2 in case of large pack sizes) of antihypertensive in the 12 months prior to or on the day of the index tofacitinib dispensing.	I10-I15
Prior myocardial infarction	Defined as ≥1 ICD-10 diagnosis code for a myocardial infarction in the 3 months prior to or on the day of the index tofacitinib dispensing.	I20-I25
Heart failure	Defined as ≥1 ICD-10 diagnosis code for heart failure in the 12 months prior to or on the day of the index tofacitinib dispensing.	I50, I110, I130 and I132
Inherited coagulation disorder	Defined as ≥1 ICD-10 diagnosis code for inherited coagulation disorder while receiving tofacitinib therapy.	D680, D681, D682, D66, D67, D689 and D686
Coronary heart disease	Defined as ≥1 ICD-10 diagnosis code for coronary heart disease.	I20-I25, I77 and Z95
Stable angina pectoris	Defined as ≥1 ICD-10 diagnosis code for stable angina pectoris.	I208 and I209
Hypercholesterolemia or dyslipidaemia or atherosclerosis	Defined as ≥1 ICD-10 diagnosis code for hypercholesterolemia or dyslipidaemia or atherosclerosis and ATC codes LLTs (statins, fibrates etc).	ICD-10: E780, E782, E783, E784, E785, E788, E789, Z863 and I70 ATC codes Statins: C10BA05, C10AA04 C10AA02, C10AA08, C10AA03, C10AA07 and C10AA01 ATC codes Fibrates: C10AB
Epstein-Barr virus (EBV)	Defined as ≥1 ICD-10 diagnosis code for Epstein-Barr virus.	D823, B348, B270, P358 and Z228
Hepatitis B virus (HBV)	Defined as ≥1 ICD-10 diagnosis code for Hepatitis B virus.	B181
Human papillomavirus (HPV)	Defined as ≥1 ICD-10 diagnosis code for HPV.	A630

Comorbidity	Definition	Codes (ICD-10 codes, ATC codes, CCAM procedure codes)
Human T-cell lymphotropic virus (HTLV)	Defined as ≥1 ICD-10 diagnosis code for human T-cell lymphotropic virus.	Z226, L303, B333 and B973
Hepatitis C virus (HCV)	Defined as ≥1 ICD-10 diagnosis code for hepatitis C virus.	B182 and B171
Coronary artery procedures*	Replacement of the ascending thoracic aorta and horizontal aorta with aortic valve replacement, with reimplantation of the coronary arteries, by thoracotomy with extracorporeal circulation	CCAM procedure code: DGKA014
	Ascending thoracic aorta replacement without aortic valve replacement, with coronary artery reimplantation, by thoracotomy with extracorporeal circulation	CCAM procedure code: DGKA003
	Replacement of the ascending thoracic aorta and horizontal aorta without aortic valve replacement, without reimplantation of the coronary arteries, by thoracotomy with extracorporeal circulation	CCAM procedure code: DGKA001
	Ascending thoracic aorta replacement with aortic valve replacement, with coronary artery reimplantation, by thoracotomy with extracorporeal circulation	CCAM procedure code: DGKA015
	Ascending thoracic aorta replacement with aortic valve replacement, without coronary artery reimplantation, by thoracotomy with extracorporeal circulation	CCAM procedure code: DGKA011
	Ascending thoracic aorta replacement without aortic valve replacement, without coronary artery reimplantation, by thoracotomy with extracorporeal circulation	CCAM procedure code: DGKA025
	Replacement of the ascending thoracic aorta and horizontal aorta without aortic valve replacement, with reimplantation of the coronary arteries, by thoracotomy with extracorporeal circulation	CCAM procedure code: DGKA026

Comorbidity	Definition	Codes (ICD-10 codes, ATC codes, CCAM procedure codes)
	Replacement of the ascending thoracic aorta and horizontal aorta with aortic valve replacement, without coronary artery reimplantation, by thoracotomy with extracorporeal circulation	CCAM procedure code: DGKA018
	Coronary revascularisation with 2 arterial and 3 venous grafts with 3 distal anastomoses, by thoracotomy with extracorporeal circulation	CCAM procedure code: DDMA005
	Coronary revascularisation using 3 arterial grafts with 3 distal anastomoses, by thoracotomy with extracorporeal circulation	CCAM procedure code: DDMA003
	Coronary revascularisation using 2 arterial grafts with 3 distal anastomoses, by thoracotomy with extracorporeal circulation	CCAM procedure code: DDMA006
	Coronary revascularisation using 2 arterial grafts with 4 or more distal anastomoses, by thoracotomy with extracorporeal circulation	CCAM procedure code: DDMA008
	Coronary revascularization with 3 arterial and 4 or more distal venous grafts by thoracotomy with extracorporeal circulation	CCAM procedure code: DDMA012
	Coronary revascularisation by arterial and venous graft with 2 distal anastomoses, by thoracotomy with extracorporeal circulation	CCAM procedure code: DDMA011

^{*} Revascularisation procedures are part of the definition of coronary artery disease. Final list of procedures will be fine-tuned based on medical advice and data distribution.

Pregnancy, ICD-10 codes

Pregnancy cessation	
Spontaneous abortion	O03
Medical abortion	O04
Other abortion	O05
Unspecified abortion	O06
Preterm labour and delivery	O60
Single delivery by forceps and vacuum extractor	O81
Single delivery by caesarean section	O82

Pregnancy cessation	ICD-10
Other assisted single delivery	O83
Multiple delivery	O84
Ectopic pregnancy	O00
Hydatidiform mole	O01
Other abnormal products of conception	O02
Failed attempted abortion	O07
Complications following abortion and ectopic and molar pregnancy	O08
Pre-existing hypertension complicating pregnancy, childbirth and the puerperium	O10
Pre-existing hypertensive disorder with superimposed proteinuria	O11
Gestational [pregnancy-induced] oedema and proteinuria without hypertension	O12
Gestational [pregnancy-induced] hypertension without significant proteinuria	O13
Gestational [pregnancy-induced] hypertension with significant proteinuria	O14
Eclampsia	O15
Unspecified maternal hypertension	O16
Haemorrhage in early pregnancy	O20
Excessive vomiting in pregnancy	O21
Venous complications in pregnancy	O22
Infections of genitourinary tract in pregnancy	O23
Diabetes mellitus in pregnancy	O24
Malnutrition in pregnancy	O25
Maternal care for other conditions predominantly related to pregnancy	O26
Abnormal findings on antenatal screening of mother	O28
Complications of anaesthesia during pregnancy	O29

Malignant cancer (except skin cancer)

ICD-	Description
10	
C00	Malignant neoplasm of lip
C01	Malignant neoplasm of base of tongue
C02	Malignant neoplasm of other and unspecified parts
C03	Malignant neoplasm of gum
C04	Malignant neoplasm of floor of mouth
C05	Malignant neoplasm of palate
C06	Malignant neoplasm of other and unspecified parts
C07	Malignant neoplasm of parotid gland
C08	Malignant neoplasm of other and unspecified major salivary glands
C09	Malignant neoplasm of tonsil
C10	Malignant neoplasm of oropharynx
C11	Malignant neoplasm of nasopharynx
C12	Malignant neoplasm of pyriform sinus

ICD- 10	Description
C13	Malignant neoplasm of hypopharynx
C14	Malignant neoplasm of other and ill-defined sites in the lip, oral cavity and pharynx
C15	Malignant neoplasm of oesophagus
C16	Malignant neoplasm of stomach
C17	Malignant neoplasm of small intestine
C18	Malignant neoplasm of colon
C19	Malignant neoplasm of rectosigmoid junction
C20	Malignant neoplasm of rectum
C21	Malignant neoplasm of anus and anal canal
C22	Malignant neoplasm of liver and intrahepatic bile
C23	Malignant neoplasm of gallbladder
C24	Malignant neoplasm of other and unspecified parts of biliary tract
C25	Malignant neoplasm of pancreas
C26	Malignant neoplasm of other and ill-defined digest
C30	Malignant neoplasm of nasal cavity and middle ear
C31	Malignant neoplasm of accessory sinuses
C32	Malignant neoplasm of larynx
C33	Malignant neoplasm of trachea
C34	Malignant neoplasm of bronchus and lung
C37	Malignant neoplasm of thymus
C38	Malignant neoplasm of heart, mediastinum and pleura
C39	Malignant neoplasm of other and ill-defined sites in the respiratory system and intrathoracic organs
C40	Malignant neoplasm of bone and articular cartilage
C41	Malignant neoplasm of bone and articular cartilage of other and unspecified sites
C45	Mesothelioma
C46	Kaposi's sarcoma
C47	Malignant neoplasm of peripheral nerves and autonomic nervous system
C48	Malignant neoplasm of retroperitoneum and peritoneum
C49	Malignant neoplasm of other connective and soft tissue
C50	Malignant neoplasm of breast
C51	Malignant neoplasm of vulva
C52	Malignant neoplasm of vagina
C53	Malignant neoplasm of cervix uteri
C54	Malignant neoplasm of corpus uteri
C55	Malignant neoplasm of uterus, part unspecified
C56	Malignant neoplasm of ovary
C57	Malignant neoplasm of other and unspecified female genital organs
C58	Malignant neoplasm of placenta

ICD- 10	Description
C60	Malignant neoplasm of penis
C61	Malignant neoplasm of prostate
C62	Malignant neoplasm of testis
C63	Malignant neoplasm of other and unspecified male genital organs
C64	Malignant neoplasm of kidney, except renal pelvis
C65	Malignant neoplasm of renal pelvis
C66	Malignant neoplasm of ureter
C67	Malignant neoplasm of bladder
C68	Malignant neoplasm of other and unspecified urinary organs
C69	Malignant neoplasm of eye and adnexa
C70	Malignant neoplasm of meninges
C71	Malignant neoplasm of brain
C72	Malignant neoplasm of spinal cord, cranial nerves and other parts of central nervous system
C73	Malignant neoplasm of thyroid gland
C74	Malignant neoplasm of adrenal gland
C75	Malignant neoplasm of other endocrine glands and related structures
C76	Malignant neoplasm of other and ill-defined sites
C77	Secondary and unspecified malignant neoplasm of lymph nodes
C78	Secondary malignant neoplasm of respiratory and digestive organs
C79	Secondary malignant neoplasm of other and unspecified sites
C80	Malignant neoplasm without specification of site
C81	Hodgkin's disease
C82	Follicular [nodular] non-Hodgkin's lymphoma
C83	Diffuse non-Hodgkin's lymphoma
C84	Peripheral and cutaneous T-cell lymphomas
C85	Other and unspecified types of non-Hodgkin's lymph
C86	Other specified types of T/NK-cell lymphoma
C88	Malignant immunoproliferative diseases
C90	Multiple myeloma and malignant plasma cell neoplasm
C91	Lymphoid leukaemia
C92	Myeloid leukaemia
C93	Monocytic leukaemia
C94	Other leukaemias of specified cell type
C95	Leukaemia of unspecified cell type
C96	Other and unspecified malignant neoplasms of lymphoid, haematopoietic and related tissue
C97	Malignant neoplasms of independent (primary), multiple

